## 6. RATIONALE AND BACKGROUND

Tofacitinib was approved by the Food and Drug Administration (FDA) in November 2012 for the treatment of adult patients with moderately to severely active rheumatoid arthritis who have had an inadequate response or intolerance to methotrexate. It may be used as monotherapy or in combination with methotrexate (MTX) or other nonbiologic disease-modifying antirheumatic drugs (NB-DMARDs).

Pfizer is currently conducting a phase 3b/4 study (A3921192) which was designed to evaluate the sustained efficacy and safety of tofacitinib modified release formulation (11 mg QD) after withdrawal of MTX versus tofacitinib modified release formulation plus continued MTX treatment in subjects with moderate to severe rheumatoid arthritis who are insufficiently responding to their stable dose of methotrexate treatment. This retrospective claims analysis is designed to compare the effectiveness and treatment patterns among tofacitinib+MTX patients who withdraw MTX vs. continue MTX in a real world setting.

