### 8.3. Cohort Assignment

Patients will be assigned to a study cohort based on MTX status following initiation of combination therapy with tofacitinib and MTX. The “MTX discontinued” cohort will contain patients who experience a gap in MTX therapy of >60 days within 12 months post-index. The “MTX interrupted” cohort will contain patients who experience a gap in MTX therapy of >60 days with 1 or more subsequent fills within 12 months post-index. The “MTX persistent” cohort will contain patients with no gap >60 days within 12 months post-index. If sample size is insufficient, the MTX “discontinued” and “MTX interrupted” cohorts may be combined.

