### 8.6.3. Treatment Patterns

- **Non-persistence.** A 0/1 flag will be created to identify if the patient is not persistent with tofacitinib before the end of the 12 month follow-up period.

Non-persistence will be identified based on a gap in treatment with the index medication or switching to another biologic.

Among patients with 1 year of follow-up, persistence through the end of the 1 year follow-up will be identified. Persistence will be identified based on the day supply (or presumed day supply) and fill dates of claims for the index medication (see [Table 2](#) for a listing of presumed day supplies). Persistence with the index medication will be defined as not having a gap in therapy of at least 60 days between fills/infusions. For retail pharmacy (RX) claims the day supply will be utilized. For Healthcare Common Procedure Coding System (HCPCS) claims a presumed day supply derived from the product label will be utilized. A gap of at least 60 days between the run-out date (service date + day supply-1) and the next service date will be considered non-persistence. Patients with early refills will be allowed to accumulate a stockpile of the index medication of up to 14 days for later use.

- **Post persistence treatment patterns.** Patients who are not persistent for the entire follow-up period will be classified into the following mutually exclusive categories based on the first occurrence of non-persistence: switch immediately, discontinue then restart, discontinue then switch, discontinue and never switch or restart.
  - **Switch immediately.** Patients will be classified as switching immediately if they initiate a non-index biologic before a 60-day gap in treatment is observed for the index medication.
  - **Discontinue then restart.** Patients will be classified as discontinuing and then restarting if there is a gap in the index therapy of at least 60 days and the first medication observed after the gap is the index medication.
  - **Discontinue then switch.** Patients will be classified as discontinuing and then switching if there is a gap in the index therapy of at least 60 days and the first medication observed after the gap is a biologic (including Tofacitinib) different from index medication.

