  - **Discontinue without switch or restart.** Patients will be classified as discontinuing without switch or restart if they have a gap in therapy of at least 60 days and there are no claims for either the index med or a different biologic for the remainder of the follow-up period.
- **Switch any time.** In addition to the 4 mutually exclusive treatment patterns, patients with a switch medication any time during the 12-month follow-up period will be identified.

- **Restart any time.** In addition to the 4 mutually exclusive treatment patterns, patients who have a claim for the index medication any time after they are considered non-persistent with the index treatment (ie, including after switching) during the 12-month follow-up, will be identified.
- **Medication Possession Ratio (MPR):** In addition to the adherence measure in the medication effectiveness assessment (see [Section 8.6.4](#)), the MPR will be evaluated for persistent patients as the total days supply between the first and including the last prescription/administration divided by the time between the first through and including last biologic prescription/administration days supply. Adherent patients will be considered those with  $MPR \geq 0.8$ . For MPR calculations, multiple prescriptions having same fill date will be treated as one prescription with longest days supply; and for all prescriptions days supply will be capped at end of follow-up. Also, the MPR will be capped at 1.0.
- **NB-DMARD adherence/addition.** Adherence with MTX and addition of a non-biologic DMARD other than MTX (sulfasalazine, hydroxychloroquine, leflunomide) during the 12 month follow-up will be identified.
  - **MTX adherence.** A single measure of adherence (PDC) will be created using all claims for MTX during the 12-month follow-up period. Adherence will be calculated as the total day supply divided by the number of days from the first claim during the follow-up until the end of the follow-up.
  - **NB-DMARD addition.** Addition of a NB-DMARD will be evaluated.

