## Secondary Objectives

- **Explore the differences in demographic and clinical characteristics among tofacitinb+MTX patients who discontinue MTX vs. persist with MTX or experience interrupted MTX.**

For this objective descriptive analysis will be conducted. The goal of this objective will be to describe the respective populations and explore the presence of demographic differences between the cohorts. Known demographic characteristics (eg, age, gender geographic location, pre-index cost and utilization) will be summarized. In addition, other patient characteristics (eg, most common comorbid diagnoses and most common medications received) will be summarized.

- **To compare RA-related costs among tofacitinb+MTX patients who discontinue MTX vs. persist with MTX or experience interrupted MTX.**

For this objective both descriptive and multivariable analysis will be conducted. For the descriptive analysis, 12-month RA-related cost measures will be presented per patient during the baseline and follow-up periods. The change in health care cost from baseline to follow-up will be identified. In addition, total RA-related health care cost will be presented in each of the months of the baseline and follow-up. The mean cost in each month will be included on a figure demonstrating the trend in costs over time. Multivariable analysis of cost will also be conducted using generalized linear models (see [Section 8.10.3](#)).

- **Compare medication effectiveness using a validated claims-based algorithm among tofacitinb+MTX patients who discontinue MTX vs. persist with MTX or experience interrupted MTX.**

Medication effectiveness at one year will be examined by the medication cohorts of interest using patients who have at least 1 year of follow-up. For this objective both descriptive analysis and multivariable analysis will be used. Descriptive analysis will focus on quantifying the percentage of patients who are effectively treated at one year. Analysis of this objective may also include multivariable analysis (eg, logistic regression). Specifically, the dependent variable will be effectively treated at one year (yes/no) and the independent variables will be study cohort, demographic characteristics, characteristics of interest, and other characteristics identified from previous objectives (see [Section 8.10.4](#)).

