### **8.11. Quality Control**

This is a retrospective study, so issues of quality control at study sites, eg, data queries, do not apply. Analyses are programmed according the specifications in the protocol, and if applicable, the statistical analysis plan and documented in a programming plan. Final deliverables are reviewed and verified by a second, independent programmer who may also perform double programming. All quality checks are documented in the programming plan.

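### Section 8.3 defines MTX discontinued without requiring that no MTX fill follows the gap, so every MTX interrupted patient also meets the definition of discontinued

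*Combined protocol and SAP*

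**What the plan says.** Section 8.3 (Cohort Assignment) sorts patients by what happens to MTX after combination therapy starts.

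- **Discontinued:** "patients who experience a gap in MTX therapy of >60 days within 12 months post-index".
- **Interrupted:** a "gap in MTX therapy of >60 days with 1 or more subsequent fills within 12 months post-index".
- **Persistent:** no such gap in the same 12 months.

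If numbers are too small, the discontinued and interrupted "cohorts may be combined".

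The cohort is then used throughout Section 8.10. In the effectiveness model, for example, "the independent variables will be study cohort, demographic characteristics, characteristics of interest" and further characteristics. Section 6 gives the aim as a comparison of "patients who withdraw MTX vs. continue MTX in a real world setting".

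For tofacitinib, Section 8.6.3 is more careful. Non-persistent patients go into "mutually exclusive categories based on the first occurrence of non-persistence", and the category for stopping without switch or restart requires that "there are no claims for either the index med or a different biologic for the remainder of the follow-up period". Those rules concern the index medication and are not applied to the MTX cohorts.

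**The concern.** The discontinued definition stops at the gap. It does not say that MTX must stay stopped, and that is the only feature that could separate a discontinued from an interrupted patient. As written, the second cohort lies wholly inside the first.

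MTX cohort is the grouping variable for the primary objective and all five secondary objectives. If the sentence is programmed as it stands, people who went back to MTX are counted as having withdrawn it, and what is reported as withdrawal becomes any MTX gap of more than 60 days. Which cohorts result then depends on coding order, which the protocol does not fix.

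A related gap is the place of interrupted patients in two-group analyses. The objectives in Section 7 and Section 8.10 name them beside persistent patients. The small-sample fallback in Section 8.3 puts them with discontinued patients. Section 6, the zero-cost check in Section 8.10.3 and the decomposition in Section 8.10.6 name only withdraw and continue.

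**Working it through.** The plan states no figure for this point, so there is none to reproduce. The check is one of set logic, confirmed by enumeration.

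**Set logic.** Let G be the patients with at least one MTX gap of more than 60 days within 12 months, and F the patients with an MTX fill after such a gap within 12 months.

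- Discontinued as written = G
- Interrupted as written = G and F
- Persistent as written = not G

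Since (G and F) is contained in G, no patient can be interrupted without also being discontinued. The intended discontinued cohort is G and not F.

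**One patient.** Take 30-day fills on days 0, 30 and 150, then monthly to the end of follow-up. The gap is 150 − (30 + 30) = 90 days, which exceeds 60, and fills follow it. This patient meets both definitions.

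**Enumeration.** Inputs: fills on days 0 and 30 (the entry rule in Section 8.2.1 requires two MTX claims without a 60-day gap), then fill or no fill in each of 10 later months, giving 2^10 = 1,024 patterns. Assumptions: 30 days' supply per fill, no stockpiling, follow-up to day 365, and a last gap counted from run-out to day 365. The counts test the rules; they are not patient shares.

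| Rule | Discontinued only | Interrupted only | Both | Persistent |
|---|---|---|---|---|
| As written, each definition applied on its own | 177 | 0 | 424 | 423 |
| One variable, discontinued tested first | 601 | 0 | 0 | 423 |
| One variable, interrupted tested first | 177 | 424 | 0 | 423 |
| Discontinued = gap and no fill after the first such gap | 177 | 424 | 0 | 423 |

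Each row sums to 1,024. As written, all 424 interrupted patterns are also discontinued (177 + 424 = 601). The last row gives the intended cohorts whatever the coding order.

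**Gap, refill, second gap.** Of the 424 interrupted patterns, 79 end in a second gap of more than 60 days. The repair has to refer to the first gap. If discontinued were worded only as a gap with no fill after it, these 79 would meet that rule on their last gap and the interrupted rule on their first: 177 discontinued only, 345 interrupted only, 79 both, 423 persistent. The current interrupted wording already covers them, because a fill followed a qualifying gap. Under the first-gap wording, 79 of the 177 + 79 = 256 patterns that end off MTX are interrupted.

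**The case against.** The strongest reply is that the intent is plain from the same paragraph. Patients are assigned to a cohort in the singular, three cohorts are named, and the option to merge two of them would mean nothing if one already contained the other. A sensible programmer would test interrupted first and obtain the intended groups. Testing discontinued first would leave a named cohort empty, which the first table would show. Section 8.11 also provides for review by a second programmer.

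Much of this stands: the fault is an omitted clause, not an unworkable design, and a correct analysis can be recovered. It does not make the written rule right. Section 8.11 says "Analyses are programmed according the specifications in the protocol, and if applicable, the statistical analysis plan and documented in a programming plan", so both programmers start from the faulty sentence. A programming plan might supply the condition, but the exposure would then be defined outside the protocol.

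A reader might go further and infer a known dilution of the results. If interrupted patients were counted in both cohorts, the discontinued-versus-interrupted mean difference would shrink to (1 − r) of its true size, where r is the share of gap patients who later refill. The document does not give r, and double counting is the coding that the text least supports, since each patient is assigned to one cohort. Against persistent patients even the direction is open, because resumers' outcomes need not lie between those of the other two groups. No bias figure is supported.

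**Conclusion.** Wrong as written, and to be corrected before the cohorts are programmed. The overlap is total: every interrupted patient meets the discontinued definition, on any data, and no section of the document removes it for MTX. This rests only on the wording of Section 8.3. The enumeration illustrates it and carries no information about patient numbers.

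The effect on results cannot be sized or signed from the document. It depends on how the rule is coded, on how many patients resume MTX and on their outcomes.

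Two stronger readings are not supported. One is that the study means to treat resumers as withdrawn; the three named cohorts and the merging fallback point the other way. The other is that patients with a gap, a refill and a second gap have no home in the plan; the interrupted definition already takes them in.

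**What to change.** In Section 8.3:

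- Define discontinued as at least one MTX gap of more than 60 days and no MTX fill after the first such gap through 12 months post-index; in short, a gap of more than 60 days and not interrupted.
- Leave the interrupted and persistent definitions as they are.
- State that the three cohorts are mutually exclusive, and that patients with a gap, a refill and a second gap are interrupted.

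In Section 8.10:

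- State that the three cohorts are reported separately.
- Say where interrupted patients go in any two-group analysis, namely the zero-cost check in Section 8.10.3 and the decomposition in Section 8.10.6 if it is used.
- If discontinued and interrupted are merged under the Section 8.3 fallback, describe the contrast as any MTX gap of more than 60 days versus none, not as withdrawal versus continuation.

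The cost is a few sentences and a few lines of code, with no extra data. The downside is that some patients who are off MTX at month 12 are classed as interrupted because they refilled once after their first gap. The report should say so.

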### 8.5. Period of Observation

All patients will be required to be continuously enrolled in the health plan for at least 24 months. Patients will have a variable length baseline period of at least 12 months. The 12 months prior to the index date will be used to assess the majority of pre-index characteristics. However, for select measures, eg, number of prior biologic therapies, and years since first RA diagnosis, the entire variable length baseline period will be utilized.

Measures utilizing the variable length baseline are noted. All baseline periods will be censored at January 1, 2012. The twelve months following the index date will be used to assess outcomes including treatment patterns, and health care costs, utilization and medication effectiveness.

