Claims are not included in the database until they have been adjudicated; there is a lag of approximately six months after the close of a calendar year or a quarter between services provided and their inclusion in the Research Databases. However, the Early View Database has a 90-day lag that includes paid amounts for 100 percent of prescription drugs, approximately 85 percent of physician office visits, and approximately 70 percent of hospital claims. The MarketScan Early View Database includes all of the components found in the standard MarketScan Commercial and Medicare Supplemental Databases. It includes standardized inpatient, outpatient, pharmaceutical, and health-plan enrollment data. The MarketScan Early View Database captures healthcare services incurred up to 90 days before data release and includes only adjudicated claims. However, the medical component of care for some patients will not be complete, since some claims (particularly inpatient claims) take longer to be adjudicated. Because this study is examining only comorbidities prior to and treatments during or prior to tofacitinib initiation fully adjudicated claims are not required and all available data will be used including Commercial, Medicare Supplemental, and Early View Databases.

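### MTX gaps and restarts are read only to month 12, so a patient's cohort depends partly on when in the year the gap began

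*Combined protocol and SAP*

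**What the plan says.** Section 8.3 (Cohort Assignment) defines three cohorts, each tied to the same 12 months:

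- Discontinued: "patients who experience a gap in MTX therapy of >60 days within 12 months post-index".
- Interrupted: "patients who experience a gap in MTX therapy of >60 days with 1 or more subsequent fills within 12 months post-index".
- Persistent: the "cohort will contain patients with no gap >60 days within 12 months post-index".

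A fallback, introduced by "If sample size is insufficient, the MTX", allows the discontinued and interrupted cohorts to be merged.

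Section 8.5 (Period of Observation) states: "All patients will be required to be continuously enrolled in the health plan for at least 24 months". At least 12 of those months are baseline, and outcomes are measured in the twelve months after index. No MTX data beyond month 12 are required or called for.

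For tofacitinib, Section 8.6.3 (Treatment Patterns) states: "Persistence with the index medication will be defined as not having a gap in therapy of at least 60 days between fills/infusions". It measures the gap from the run-out date to the next service date. It also counts a switch to another biologic as non-persistence.

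I found no look-forward past month 12, no rule for a gap still open at that point, and no sensitivity analysis on it. The limitations in Section 8.12 do not mention it.

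**The concern.** The window that assigns MTX status closes for everyone on the same follow-up day, but patients enter a gap at different times. A gap that begins early has many months in which to pass 60 days and then show a refill. A gap that begins in month 9 or 10 has little time to show a refill, and one that begins later still cannot pass 60 days at all. The label therefore reflects the time left in the year as well as what the patient did.

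Every objective compares withdrawn MTX with persistent or interrupted MTX. If some permanent stoppers sit in the persistent cohort and some restarters sit in the discontinued cohort, both contrasts are blurred. Discontinued and interrupted would also differ by construction in the timing of the gap. Because outcomes are measured over the same 12 months, that timing also sets how much of the outcome year is spent off MTX.

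**Working it through.** The plan states no stop rate, restart rate or sample size, so there is no figure to reproduce. The check applies the Section 8.3 rules day by day.

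**Conventions.** Index is day 0 and follow-up is days 0–364. Run-out day *r* is the last covered day. Section 8.6.3 measures gaps from run-out for tofacitinib; I assume the same for MTX, since Section 8.3 does not say. The cohorts are treated as exclusive, which seems intended. Read literally, the discontinued definition has no condition excluding a later fill, so interrupted patients also meet it.

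**Late stops.** Uncovered days visible by the end of follow-up are 364 − *r*. A gap >60 days is visible only if 364 − *r* > 60, so *r* ≤ 303. A permanent stop with run-out on days 304–364 (61 days) is labelled persistent.

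**Late restarts.** For a gap of *g* uncovered days, the refill falls on day *r* + *g* + 1.

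- Interrupted: *r* + *g* + 1 ≤ 364, so *r* ≤ 363 − *g*.
- Discontinued: 364 − *g* ≤ *r* ≤ 303, which is *g* − 60 possible run-out days.
- Persistent: *r* ≥ 304.

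For an 80-day gap:

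| Run-out day | Refill day | Uncovered days seen | Label |
|---|---|---|---|
| 100 | 181 | 80 | Interrupted |
| 290 | 371 | 74 | Discontinued |
| 320 | 401 | 44 | Persistent |

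**Share of stops in the blind period (assumed timing).**

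- Uniform run-out from day 0: 61/365 = 16.7%.
- From day 30: 61/335 = 18.2%.
- From day 60: 61/305 = 20.0%.
- From day 90: 61/275 = 22.2%.
- Exponential timing with 30%, 50% or 70% stopping per year, from the same start days: 9.6% to 19.9%.

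The overall range is about 10–22%.

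**Share of the persistent cohort (assumed: 30% or 50% of patients stop without restarting, 18% of them in the blind period).**

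- 30% stop: 0.30 × 0.18 / (0.70 + 0.30 × 0.18) = 0.054/0.754 = 7%.
- 50% stop: 0.50 × 0.18 / (0.50 + 0.50 × 0.18) = 0.090/0.590 = 15%.

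**Share of restarters labelled discontinued (assumed: uniform run-out on days 60–364, 305 days).** The share is (*g* − 60)/305.

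| Gap length (days) | Calculation | Share |
|---|---|---|
| 75 | 15/305 | 4.9% |
| 90 | 30/305 | 9.8% |
| 120 | 60/305 | 19.7% |
| 180 | 120/305 | 39.3% |

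In each case a further 61/305 = 20% are labelled persistent.

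As a cross-check, take gap starts uniform on days 30–365 and an exponential restart delay with mean *m* days after day 60 of the gap. Among restarters whose gap passes 60 days in the year, the share labelled discontinued is (*m*/275)(1 − e^(−275/*m*)). That is 22% for *m* = 60 and 39% for *m* = 120.

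**Tofacitinib.** The rule is a gap of at least 60 days: 364 − *r* ≥ 60, so *r* ≤ 304. A later stop without a switch counts as persistent.

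**The case against.** **Completion of the gap by day 365 is not written.** A gap within 12 months could mean one that begins in that time. This reading would rescue the late stops, though it needs claims to about month 14, which Section 8.5 does not require. It does not rescue the late restarts, because the refill is expressly limited: "with 1 or more subsequent fills within 12 months post-index". The ambiguity itself needs settling.

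**The labels partly describe real exposure in the outcome year.** A patient covered to day 320 was on MTX for most of it. One who ran out on day 290 and refilled on day 371 had none for the rest of it. The MTX adherence measure in Section 8.6.3 also runs to the end of follow-up and so reflects a late stop. This stands. A reader might infer that the cohorts are simply misclassified and that later claims should reassign everyone whose gap starts by day 365. The documents do not support that: such a rule would move patients covered for nearly the whole outcome window out of persistent, using events after that window.

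**The tofacitinib rule is broader than a gap.** A reader might infer that 12-month tofacitinib persistence is really persistence to month 10. That is too strong. A patient who stops on day 320 and switches on day 340 is non-persistent under Section 8.6.3, and the year-long tofacitinib PDC in Section 8.6.4 reflects uncovered days.

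**Merging the cohorts is allowed.** It would remove the late-restart problem, but only if the sample is judged insufficient, and it leaves the late stops.

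**The sizes rest on assumptions.** This stands. The shares near 39% need long gaps; at 75–90 days the figure is 5–10%.

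**Conclusion.** The concern holds in a limited form. The truncation follows from Sections 8.3 and 8.5 on the natural reading, and the late-restart part follows on either reading while the two gap cohorts are kept apart.

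Under assumed timing, about 10–22% of stops fall in the blind period. That is about 7–15% of the persistent cohort if 30–50% of patients stop. About 5–39% of restarters are labelled discontinued, depending on gap length. None of these percentages comes from the documents. The dependence of the label on timing does not rest on them; its size does.

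For tofacitinib, the same truncation applies only to late stops without a switch. This is a weakness in the exposure definition that should be repaired before the cohorts are programmed. It is not a reason to abandon the 12-month outcome window.

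**What to change.** Keep outcomes at 12 months and amend Section 8.3 as follows.

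1. State whether the >60-day gap must begin or be completed by day 365, and how MTX run-out is measured. State that discontinued excludes patients with a qualifying refill.
2. Separate interrupted from discontinued by one fixed restart window counted from run-out, the same for every patient, with its length prespecified.
3. Put patients whose gap is still open and cannot be followed that long in a group called late gap, undetermined. At a minimum, do this in a prespecified sensitivity analysis that removes them from the persistent and discontinued cohorts.
4. Use pharmacy claims after day 365 only as a sensitivity analysis in patients still enrolled. Do not use them in the main analysis to move patients covered to nearly day 365 out of persistent.
5. Describe gap-based MTX and tofacitinib persistence as confirmed to about day 305.

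**Feasibility of item 4.** Section 8.7.1 says the Early View data "includes paid amounts for 100 percent of prescription drugs". If claims run to 31 January 2018 (assumed: 12 months after the last index date), 60 extra days reach index dates to about the start of December 2016, or about 35 of 37 index months. A window of 120 extra days reaches about 3 October 2016, or about 33 of 37. Enrolment past month 12 is not guaranteed.

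**Cost.** The work is definition wording and programming. The downside is an undetermined group and somewhat smaller cohorts, in a study that Section 8.10.6 already expects to be relatively small. A short window helps keep that group small. For illustration, with uniform run-outs on days 60–364 and no later claims, a 120-day window leaves run-outs on days 245–364 unresolved, which is 120/305 = 39% of permanent stops. A 90-day window leaves 90/305 = 30%.
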